### 7.5.2 Withdrawals from Investigational Product

Discontinuation of investigational product, but continued follow-up visits, including efficacy and safety evaluations. Standard reasons for withdrawing from taking further investigational product, but continuing follow-up visits and safety evaluations may be:

- Unacceptable AEs
- Patient request
- Investigator's discretion
- Intercurrent illness
- Pregnancy

Patients who develop Grade 3 or higher National Cancer Institute Common Terminology Criteria or Adverse Events (NCI-CTCAE), or who experience a 2-point worsening of m-SOFA criteria, that is determined to be possibly or probably attributable to the study drug will be discontinued.

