## **7.8 Stopping Criteria**

Trial will be stopped if more than one patient has a grade 3 or higher AE on the CTCAE scale in any one category that is determined to be possibly or probably attributable to study drug (exclusion evaluation of liver function).

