### 11.1.2 Severity

The intensity of an AE is an estimate of the relative severity of the event made by the Investigator based on his or her clinical experience. The following definitions are to be used to rate the severity of an AE:

- Mild: the AE is transient and easily tolerated.
- Moderate: the AE causes the patient discomfort and interrupts the patient's usual activities.
- Severe: the AE causes considerable interference with the patient's usual activities, and may be incapacitating or life-threatening.

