### 11.1.3 Relationship to IMP

The Investigator will establish causality of the AE to experimental treatment. The Investigator should take into account the patient's history, most recent physical examination findings, and concomitant medications.

The following definitions will be used to determine causality of an AE:

- Not related: temporal relationship of the onset of the AE, relative to the experimental treatment is not reasonable or another cause can explain the occurrence of the AE.
- Related: temporal relationship of the onset of the AE, relative to the experimental treatment is reasonable, follows a known response pattern to the treatment, and an alternative cause is unlikely.

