### **13.10 End of Trial**

The end of trial is defined as 'last patient last visit (LPLV)'. LPLV is defined as the date the Investigator reviews the last subject's safety data and determines that no further evaluation is required for the subject to complete the trial.

The study will be prematurely terminated should more than one patient experience a Grade 3 or higher AE on the CTCAE scale in any one category that is determined to be possibly or probably attributable to study drug (excluding evaluation of liver function), or a 2-point worsening of modified m-SOFA score if possibly or probably attributable to study drug.

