6.16 Safety Evaluation

6.16.1 Adverse Events

Adverse events (AEs) will be coded using the latest MedDRA dictionary version. The version used will be indicated in the data summaries and listings.

A treatment-emergent adverse event (TEAE) is defined as an AE that started on or after the start of the administration study treatment. If adverse event dates are incomplete and it is not clear whether the adverse event was treatment-emergent, it will be assumed to be treatment-emergent.

Any AE commencing after the last administration of study treatment may be considered treatment emergent.

A summary table by treatment and overall will present the following:

- TEAEs (events and patients).
- Serious TEAEs (events and patients).
- Serious study treatment related TEAEs (events and patients).
- TEAEs by pattern (intermittent/continuous/single event) (events and patients).
- TEAEs by severity (mild/moderate/severe) (events and patients).
- TEAEs by relationship to study treatment (events and patients).
- TEAEs leading to withdrawal from study (patients only).
- TEAEs leading to discontinuation of study treatment (patients only).
- Study treatment related TEAEs leading to discontinuation of study treatment (patients only).
- TEAEs leading to death (patients only).

In the above summaries, if a patient experienced more than one TEAE, the patient will be counted once using the most related event for the “by relationship to study treatment” and “related to study treatment” summaries and at the worst severity for the “by severity” summary. If a patient experienced more than one TEAE, the patient will be counted once for each pattern recorded. For summaries at the patient level, the number and percent of patients will be presented.

The above summary table will be presented for the pilot and double-blind phases.

The following tables will be presented:

- TEAEs by System Organ Class (SOC) and Preferred Term (PT).
- TEAEs by PT.
- TEAEs by SOC, PT and severity.
- TEAEs by SOC, PT and relationship to study treatment (related/ not related).
- Serious TEAEs by SOC and PT
- TEAEs leading to withdrawal by SOC and PT

For all of the above, SOC and PT will be presented in decreasing frequency of the total number of patients with TEAEs. Number of events and number and percentage of patients will be presented.

Further details of the above four tables are given below:

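### The mandatory safety stop in Protocol 7.8 and 13.10 has no allocation check, so in the double-blind phase events in placebo patients can end the trial

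*Protocol*

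**What the plan says.** Protocol 7.8: "Trial will be stopped if more than one patient has a grade 3 or higher AE on the CTCAE scale in any one category". The events must be judged possibly or probably attributable to study drug, and evaluation of liver function is excluded.

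Protocol 13.10: "The study will be prematurely terminated should more than one patient experience a Grade 3 or higher AE on the CTCAE scale", with the same attribution condition and the same liver-function exclusion. It then adds "or a 2-point worsening of modified m-SOFA score if possibly or probably attributable to study drug". Protocol 7.8 has no such clause.

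Both sections are mandatory in wording. Neither is limited to the pilot or to DS102 recipients, and neither mentions the DSMB, unblinding or a comparison by arm.

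Other sections that bear on the rule:

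- Protocol 11.1.3 gives causality to the investigator. Under "The following definitions will be used to determine causality of an AE" it lists two levels, related and not related.
- Protocol 11.1.2, under "The following definitions are to be used to rate the severity of an AE", lists mild, moderate and severe. SAP 6.16.1 tabulates adverse events on these two scales.
- Protocol 7.5.2 stops drug in a single patient for an attributed CTCAE grade 3+ event, "or who experience a 2-point worsening of m-SOFA criteria, that is determined to be possibly or probably attributable to the study drug".
- Protocol 12.4 keeps site, monitoring and conduct staff blinded until database lock, emergencies apart.
- Protocol 11.2.2 has SUSARs reported unblinded to authorities and ethics committees.
- Protocol 13.3 lets the DSMB recommend continuing, modifying or ending the study, and leaves its detailed role to a charter.

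**The concern.** A rule meant to protect patients from DS102 counts events by a judgement made without knowing who received DS102. A placebo patient's sepsis or renal failure that a blinded investigator thinks possibly drug-related counts like any other. Two such patients, or one in each arm, meet the threshold, and the text then leaves no discretion. The trial could end before its efficacy and safety comparison is complete, on events that DS102 cannot have caused.

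It is also not settled which events count. The rule needs a CTCAE grade and a possible/probable attribution, and the AE section asks for neither. A reader of 7.8 alone would not know of the m-SOFA trigger. A reader of 13.10 cannot tell whether one patient is enough for it. If one is enough, the event that takes a single patient off drug under 7.5.2 would also end the trial.

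**Working it through.** **Reading the text.** In the open-label pilot all six patients receive DS102, so the gap does not arise. In the double-blind phase the steps are: threshold met (7.8, 13.10); attribution made by the investigator (11.1.3); investigator blinded (12.4); stop mandatory. No step uses allocation.

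**Scales side by side.**

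| | Stop rule (7.8, 13.10) | AE section (11.1.2, 11.1.3) |
|---|---|---|
| Severity | CTCAE grade 3 or higher | mild / moderate / severe |
| Causality | possibly or probably | related / not related |

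Related in 11.1.3 requires that another cause be unlikely, which is stricter than possibly. The definition of an adverse reaction in 11.2.1 (relationship cannot be ruled out) is closer, but the stop rule does not refer to it.

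**Arithmetic.** The plan gives no operating characteristics for the rule, so there is no figure to reproduce.

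*Who is in a triggering pair.* Inputs: 60 patients per arm (Protocol 12.2), an inert drug, attribution unrelated to arm, exactly two flagged patients.

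- Both on placebo: C(60,2)/C(120,2) = 1,770/7,140 = 24.8%.
- One in each arm: 60 × 60/7,140 = 50.4%.
- At least one on placebo: 24.8% + 50.4% = 75.2%.

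This is a consequence of 1:1 allocation and is conditional on a stop. It says nothing about how likely a stop is.

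*How often the rule fires (illustrative only).* Let t be the share of patients with an attributed grade 3+ event, spread evenly over k independent categories. Both are assumptions; the documents give neither. Then

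P(stop) = 1 − [P(Bin(N, t/k) ≤ 1)]^k.

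N = 126 counts everyone, six pilot patients included. N = 66 counts only those on DS102 (60 + 6).

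Example with t = 1%, k = 10, so 0.001 per category:

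- N = 126: 0.999^126 + 126 × 0.001 × 0.999^125 = 0.8816 + 0.1112 = 0.9927 (from unrounded terms), and 1 − 0.9927^10 = 7%.
- N = 66: 0.9361 + 0.0618 = 0.9979, and 1 − 0.9979^10 = 2%.

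| t (expected patients of 126) | All 126, k = 5 / 10 / 20 | 66 on DS102, k = 5 / 10 / 20 |
|---|---|---|
| 0.5% (0.6) | 4 / 2 / 1% | 1 / 0.5 / 0.3% |
| 1% (1.3) | 13 / 7 / 4% | 4 / 2 / 1% |
| 2% (2.5) | 38 / 24 / 14% | 14 / 8 / 4% |
| 5% (6.3) | 89 / 76 / 56% | 53 / 36 / 22% |

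*Protection if only DS102 patients count.* Take one category, 66 patients on DS102 at rate r and 60 on placebo at rate b, and compute P(two or more events).

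| r on DS102 | Either rule, b = 0 | As worded, b = 1% | DS102 only, b = 1% |
|---|---|---|---|
| 2% | 38% | 57% | 38% |
| 5% | 85% | 91% | 85% |
| 10% | 99% | 99.5% | 99% |

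A toxicity confined to DS102 is stopped equally often under either rule. The difference arises when placebo patients also have attributed events in that category.

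**The case against.** A conservative stop that needs no unblinding is a defensible choice in an exploratory phase II trial in critically ill patients, and counting fewer patients gives up some protection (57% against 38% in the 2% and 1% case). That cost is real and belongs in the fix.

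Other sections partly fill the gaps. Protocol 11.1.3 says who judges causality, 7.5.2 already requires sites to apply CTCAE, and 11.2.1 comes close to defining possibly. The eCRF is not visible and may hold the needed items. The liver-function exclusion removes events that would be common in this disease. All of this narrows the point; none of it adds an arm check.

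Study drug might be read as DS102 only, as 12.2 uses it for the pilot. The same section also speaks of study drug assignments in the randomised phase, and a blinded judgement cannot apply the narrower reading in any case.

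Three stronger readings are tempting, and the documents do not support them:

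- *Three in four stops would be spurious.* The 75% assumes an inert drug and a stop that has already happened, and two-thirds of it (50 of 75 points) is pairs that also contain a DS102 patient.
- *The trial is likely to be stopped by placebo events.* That needs an attributed-event rate. Protocol 1.6 reports no SAEs in the healthy-volunteer study and no related SAEs so far in the phase II studies, which points low but comes from other populations. Protocol 1.1 describes multi-organ failure, sepsis and mortality above 30%, which points to many severe background events without saying how many would be attributed.
- *Nobody could learn the allocation.* Unblinded SUSAR reporting and IWRS access for pharmacovigilance monitors exist, and the DSMB charter may provide a check. The gap is that 7.8 and 13.10 do not use any of these.

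**Conclusion.** The point holds as a fault in a stated rule. As worded, the mandatory stop can be met wholly or partly by placebo patients' events, with no step that looks at allocation. This follows from the text and needs no assumed rate. It would be answered only if the unseen charter contains such a check, in which case the protocol should say so.

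The size is uncertain. With 10 or more equal categories and attributed rates of 1% or below, P(stop) for an inert drug is at most 7%, and no more than about 5 points above DS102-only counting. With five categories it is 13% at a 1% rate. It grows quickly from 2%. These figures rest entirely on assumed rates, equal and independent categories, and attribution unrelated to arm.

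The mismatch of scales and the m-SOFA clause present in 13.10 alone are drafting faults that stand on their own. Protocol 13.10 adds a trigger to 7.8; the two do not contradict each other on the AE criterion. This should be corrected, though it does not undermine the design.

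**What to change.** State one rule, in the same words, in 7.8 and 13.10:

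1. Reaching the blinded threshold pauses enrolment and dosing and triggers prompt DSMB review of the flagged cases by actual allocation.
2. The trial must stop if more than one DS102-treated patient meets the AE criterion. The DSMB may recommend stopping on fewer. The CTCAE grade and the liver-function exclusion stay as they are.
3. Put the m-SOFA trigger in both sections and state how many patients it requires. That number is a clinical decision and should not be inherited from the AE criterion by default.
4. Record CTCAE grade and possible/probable attribution for each event and name the assessor, or restate the rule on the 11.1 scales.

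The cost is amended wording in two sections, a matching charter entry if there is none, and two AE items if the eCRF lacks them. The DSMB already exists, and 11.3.1 already uses independent review within 24 hours for possible liver injury.

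Downsides:

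- The DSMB sees allocation for the flagged cases.
- Continuing implies that at least one flagged case was on placebo.
- One DS102 case plus one placebo case no longer stops the trial automatically; the pause limits exposure while the DSMB decides.
- Chance stops from DS102 events alone remain (8% at an assumed 2% rate and 36% at 5%, with 10 categories).
- The pause needs a time limit, because SAP 6.4 drops patients who miss more than three consecutive days of dosing from the per-protocol set.

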## 8 STUDY CONDUCT

### 8.1 Study Schedule

During the study, 8 visits to the clinic are scheduled after the screening visit (Visit 1): one at the start of the comparative treatment period (Baseline/Visit 2) and six in the comparative treatment period (Visit 3/Day 3, Visit 4/Day 5, Visit 5/Day 7, Visit 6/Day 14, Visit 7/Day 21, Visit 8/Day 28 or Early Termination).

A final safety follow-up visit (Visit 9/Day 90) will be conducted on Day 90.

For patients who discontinue the study early, for whatever reason, the Early Termination visit (Visit 8) will be performed. Patients who discontinue the study before Day 28 and are already discharged from the hospital will be asked to attend the investigative site as soon as possible that assessments scheduled for Visit 8 can be conducted. These patients will be asked also to attend a final safety follow-up visit (Visit 9/Day 90).

### 8.2 Clinic Visits

A tabulated flow chart of the study is presented in Appendix 1 and 2.

#### 8.2.1 Screening Visit (Visit 1)

The patient must sign and date the informed consent form (ICF) before any study-specific procedures are conducted.

Once informed consent has been obtained, the Investigator will assign a patient screening number. The following screening assessments/sample collections will be performed:

- Verification of inclusion/exclusion criteria (Sections 7.2 & 7.3)
- Demographic data
- Medical history (as detailed in Section 9.2.1)
- History of alcohol abuse for at least six months documented
- Physical examination (as detailed in Section 9.2.2)
- Liver ultrasound (as detailed in Section 9.2.11)
- Vital signs (blood pressure, heart rate and body temperature)(as detailed in Section 9.2.4)
- Electrocardiogram (ECG) (as detailed in Section 9.2.3)
- Samples for clinical laboratory safety tests (haematology, serum biochemistry, coagulation tests and plasma caeruloplasmin as detailed in Section 9.2.5)
- Virology (as detailed in Section 9.2.6)
- Urinalysis (as detailed in Section 9.2.15)

- Pregnancy test (as detailed in Section 9.2.7)
- MELD (as detailed in Section 9.1.1)
- MDF (as detailed in Section 9.1.7)
- West Haven criteria assessment (as detailed in Section 9.1.11)
- )
- Total bilirubin (as detailed in Section 9.1.2)
- AST:ALT (as detailed in Section 9.1.3)
- Concomitant medication assessment (as detailed in Section 9.2.10)

All procedures that are medically necessary should be followed.

### **8.2.2 Treatment Period**

Following completion of a successful screening visit, patients will begin the comparative treatment period (28 days).

At the start of the comparative treatment period, after confirmation of continued eligibility, patients will be randomly assigned to one of the two treatment regimens.

Patients will take the allocated investigational medicinal product (IMP) to which he/she is allocated twice-daily, in the morning and in the evening, within 30 minutes after a meal, throughout the comparative treatment period. Each administration of IMP will be recorded in the eCRF/hospital records or in a patient diary card, if discharged before day 28 of the study.

Patients who discontinue the study early will have all study procedures scheduled for Visit 8 (see Section 8.2.9) performed as soon as possible after patient withdrawal so that all study-related information can be recorded.

Counselling on alcohol consumption should be performed during the study. In-study and post-discharge referral and intervention will be provided as needed.

### **8.2.3 Baseline (Visit 2)**

The following assessments/sample collections will be performed at Baseline/Visit 2:

- Verification of inclusion/exclusion criteria (as detailed in Sections 7.2 & 7.3)
- Medical history (as detailed in Section 9.2.1)
- Physical examination (as detailed in Section 9.2.2)
- Vital signs (blood pressure, heart rate and body temperature)(as detailed in Section 9.2.4)
- ECG (as detailed in Section 9.2.3)
- Pregnancy test(as detailed in Section 9.2.7)
- Pharmacokinetic sampling (as detailed in Section 9.2.8.1)
- Exploratory blood sampling (as detailed in Section 9.2.8.2)

- Samples for clinical laboratory safety tests (haematology, serum biochemistry, and coagulation tests as detailed in Section 9.2.5)
- MELD ( as detailed in Section 9.1.1)
- MDF (as detailed in Section 9.1.7)
- m-SOFA (as detailed in Section 9.1.8)
- APACHE II score(as detailed in Section 9.1.9)
- Total bilirubin (as detailed in Section 9.1.2)
- CK-18 (as detailed in Section 9.1.6)
- AST:ALT (as detailed in Section 9.1.3)
- Child pugh score (as detailed in Section 9.1.5)
- Gamma GT (as detailed in Section 9.1.4)
- West Haven criteria assessment (as detailed in Section 9.1.11)
- Lille score assessment (as detailed in Section 9.1.10)
- Collection of acute kidney injury, ascites and variceal haemorrhage data
- AE assessment (as detailed in Section 11)
- Concomitant medication assessment (as detailed in Section 9.2.10)

#### Biomarker (as detailed in Section 9.2.8.3)

In addition, the following assessments of nutritional status will also be performed, with nutritional interventions provided where required:

- BMI
- Bedside Subjective Global Assessment (SGA) score (0, 1, 2, and 3). Patients will be classified into the following categories:
  - Well nourished (0)
  - Mild malnutrition (1)
  - Moderate malnutrition (2)
  - Severe malnutrition (3)

If all study entry criteria are satisfied the Investigator will randomise the patient and provide the patient with the designated IMP or placebo from one of the patient treatment packs available at the site.

The first dose of IMP or placebo will be administered at site once all baseline assessments have been completed. The patient will take their second dose of IMP or placebo in the evening of Day 0. The capsules will then be administered twice-daily.

#### 8.2.4 Visit 3/Day 3

The following assessments will be performed:

- Physical examination (as detailed in Section 9.2.2)
- Vital signs (blood pressure, heart rate and body temperature), as detailed in Section 9.2.4)

- Pharmacokinetic sampling (as detailed in Section 9.2.8.1)
- Samples for clinical laboratory safety tests (haematology, serum biochemistry, and coagulation tests as detailed in Section 9.2.5)
- MELD (as detailed in Section 9.1.1)
- MDF (as detailed in Section 9.1.7)
- m-SOFA (as detailed in Section 9.1.8)
- APACHE II score (as detailed in Section 9.1.9)
- Total bilirubin (as detailed in Section 9.1.2)
- CK-18 (as detailed in Section 9.1.6)
- AST:ALT (as detailed in Section 9.1.3)
- Child pugh score (as detailed in Section 9.1.5)
- Gamma GT (as detailed in Section 9.1.4)
- Collection of acute kidney injury, ascites and variceal haemorrhage data
- AE assessment (as detailed in Section 11)
- Concomitant medication assessment (as detailed in Section 9.2.10)
- Biomarker (as detailed in Section 9.2.8.3)
- Lille Score (as detailed in Section 9.1.10)
- West Haven criteria assessment (as detailed in Section 9.1.11)

### 8.2.5 Visit 4/Day 5

The following assessments will be performed:

- Physical examination (as detailed in Section 9.2.2)
- Vital signs (blood pressure, heart rate and body temperature), as detailed in Section 9.2.4)
- Pharmacokinetic sampling (as detailed in Section 9.2.8.1)
- Samples for clinical laboratory safety tests (haematology, serum biochemistry, and coagulation tests as detailed in Section 9.2.5)
- MELD (as detailed in Section 9.1.1)
- MDF (as detailed in Section 9.1.7)
- m-SOFA (as detailed in Section 9.1.8)
- APACHE II score (as detailed in Section 9.1.9)
- Total bilirubin (as detailed in Section 9.1.2)
- CK-18 (as detailed in Section 9.1.6)
- AST:ALT (as detailed in Section 9.1.3)
- Child pugh score (as detailed in Section 9.1.5)
- Gamma GT (as detailed in Section 9.1.4)
- AE assessment (as detailed in Section 11)
- Collection of acute kidney injury, ascites and variceal haemorrhage data
- Concomitant medication assessment (as detailed in Section 9.2.10)
- West Haven criteria assessment (as detailed in Section 9.1.11)

---

- Biomarker (as detailed in Section 9.2.8.3)
- Lille Score (as detailed in Section 9.1.10)

### 8.2.6 Visit 5/Day 7

The following assessments will be performed:

- Physical examination (as detailed in Section 9.2.2)
- Vital signs (blood pressure, heart rate and body temperature), as detailed in Section 9.2.4)
- Pharmacokinetic sampling (as detailed in Section 9.2.8.1)
- Samples for clinical laboratory safety tests (haematology, serum biochemistry, and coagulation tests as detailed in Section 9.2.5)
- MELD ( as detailed in Section 9.1.1)
- MDF (as detailed in Section 9.1.7)
- m-SOFA (as detailed in Section 9.1.8)
- APACHE II score (as detailed in Section 9.1.9)
- Total bilirubin (as detailed in Section 9.1.2)
- CK-18 (as detailed in Section 9.1.6)
- AST:ALT (as detailed in Section 9.1.3)
- Child pugh score (as detailed in Section 9.1.5)
- Gamma GT (as detailed in Section 9.1.4)
- West Haven criteria assessment (as detailed in Section 9.1.11)
- Lille score assessment (as detailed in Section 9.1.10)
- Collection of acute kidney injury, ascites and variceal haemorrhage data
- AE assessment (as detailed in Section 11)
- Concomitant medication assessment (as detailed in Section 9.2.10)
- Biomarker (as detailed in Section 9.2.8.3)

### 8.2.7 Visit 6/Day 14

The following assessments will be performed:

- Physical examination (as detailed in Section 9.2.2)
- Vital signs (blood pressure, heart rate and body temperature), as detailed in Section 9.2.4)
- Pharmacokinetic sampling (as detailed in Section 9.2.8.1)
- Exploratory blood sampling (as detailed in Section 9.2.8.2)
- Samples for clinical laboratory safety tests (haematology, serum biochemistry, and coagulation tests as detailed in Section 9.2.5)
- MELD ( as detailed in Section 9.1.1)
- MDF (as detailed in Section 9.1.7)
- m-SOFA (as detailed in Section 9.1.8)
- APACHE II score(as detailed in Section 9.1.9)
- Total bilirubin (as detailed in Section 9.1.2)

- CK-18 (as detailed in Section 9.1.6)
- AST:ALT (as detailed in Section 9.1.3)
- Child pugh score (as detailed in Section 9.1.5)
- Gamma GT (as detailed in Section 9.1.4)
- West Haven criteria assessment (as detailed in Section 9.1.11)
- Lille score assessment (as detailed in Section 9.1.10)
- Total bilirubin (as detailed in Section 9.1.2)

